****Updated to add changes in inclusionary criteria**

****Updated July 15, 2025 – Includes statistical analysis plan.**

Human Subjects Involvement, Characteristics, and Design

The study is a Phase I clinical trial that employs a randomized parallel design. We plan to enroll 160 children diagnosed with Developmental Language Disorder and their caregivers who will provide services to approximately half of these children. We predict that 15% of the children (N=20) will be lost to follow-up, thus we enroll 160, in order to have 140 children complete the entire study and meet the planned enrollment goals. Children will be randomly assigned to one of four treatment conditions, thus we expect 35 participants per condition. Research will be carried out at the University of Delaware and the University of Maryland College Park.

Children with Developmental Language Disorder (N = 160)

Inclusionary & Exclusionary Criteria:

- Age: 4-7 years old
- Primarily English speaking: Less than 20% exposure to another language, per parent report
- Document poor syntax skills: standard score below 85 on the DELV-NR composite, a dialect neutral assessment (Seymour, Roeper, de Villiers, & De Villiers, 2005).
- Nonverbal IQ within typical range: t-score at or above 35 on the DAS, matrices subscale, (Elliott, 2007).
- Hearing within the typical range: Pass screening using SoundScouts (Gumbie et al., 2018; Mealings et al., 2020) or provide reports of passing a hearing screening at school or in a pediatrician's office. *Due to COVID and limitations on in person activities, treatment may proceed even if these reports are not obtained if no one has concerns about hearing and we will track/follow up with families to obtain a clear hearing screening within 12 months of completion of intervention. Documentation of how many children did not complete hearing screenings will be retained and inform interpretation of data.
- No diagnosis of Autism: Cutoff score of 15 on the SCQ, (Rutter, Bailey, & Lord, 2003)
- No diagnosis of significant sensory-motor concerns or significant psychiatric disorders per parent report
- Able to benefit from treatment:
 - Score below 60% correct on experimenter developed elicited production probes of passives and object relative clauses
 - Producing simple transitive sentences (SVO) and MLU of 2.5 on 100 utterance language sample

Caregivers of Children with DLD (N=160)

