Second, for each time window (early and late), we will assess the extent to which Treatment Condition affects interpretation of the treated noncanonical structure. Our dependent variable will be **Structural Sensitivity**, calculated as *an averaged difference score of Agent Preference in the canonical structure (SRC, active) minus the noncanonical structure for each structure (ORC, passive) for each child.* This measure is selected rather than Agent Preference because it captures the **degree to which a child differentiates the two structures** from each other. Sensitivity to passive/object relative clause cues will be evident in values greater than 0, with higher values mapping onto increased sensitivity. Each child will receive a single Structural Sensitivity score for active/passives and a single Structural Sensitivity score for subject/object relative clauses at each test point.

Analytic Approach

For both comprehension and production outcomes, we utilize generalized linear mixed models to examine change over time for each condition. The adoption of generalized linear mixed models (GLMM) with random effects for subjects and items as the statistical approach has advantages in that we do not need to exclude children for failing to produce scorable responses given that this model can account for uneven response rates across children (Baayen, Davidson, & Bates, 2008) and it accounts for item level variance that can affect results.

Production probe accuracy will be analyzed with a logit link function. Use of a logit link function for production data also closely mirrors the underlying data structure in which individual items are scored as correct or incorrect. Structural sensitivity will be analyzed with linear mixed-effects models. Maximal models will include random intercepts (and possibly random slopes) for subjects, items, and clause type (Barr, Levy, Scheepers, & Tily, 2013), and parameter-specific p-values will be estimated with degrees of freedom determined through Satterthwaite approximation (Luke, 2017).

We will model comprehension and production outcomes separately, though we make similar predictions as to the effect of treatment on each outcome measure. Prior to carrying out the main analyses, we will check for differences attributable to participant sex and race (relevant biological variables). These will be included in future analyses if necessary, but prior work suggests that they are not likely to influence outcomes.

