We will also use generalized additive mixed models (GAMMs) to model longitudinal patterns in eyetracking data (i.e., looks to the agent) to examine and visualize timing of stimulus effects and changes in focus at key points during and after presentation of the prompt. GAMMs model fixations as an intensive time series (Cho et al., 2018, 2022) and allow identification of key points of separation. Moreover, the GAMMs models do not require prespecification of windows of time, providing more flexibility and sensitivity when modeling differences in eyetracking over time and between groups. The specification of the GAMMs models will mirror the GLMM equations below, except that smoothing functions will be used for an additional TIME predictor to fit a spline regression for each time series.

Aim 1. Determine the relative differences in the efficacy of illustrated syntax stories and recast therapy when treatment is dose controlled and delivered by highly trained SLPs in the laboratory.

We will first confirm that we achieved control of dose in the two in-lab conditions. We will carry out an unpaired two-tailed t-test comparing the estimated dose delivered for each condition. We anticipate that the two conditions will not differ and that the distributions will show high degrees of overlap ($p>.5$, $d<.3$).

To test the key question in Aim 1, we will compare the relative effect of treatment condition by testing for differences between the treatment effect estimates of stories in the lab and recasts in the lab conditions.

Well-matched groups at pretest will be evident if the two conditions do not differ at pre-test. If one treatment condition is more effective than the other, this should be evidenced by an interaction between test point and treatment contrast effects that are significant at the p<.05 level; if, as we hypothesize, the two conditions are equally effective there will be no significant interaction between test point and treatment. We are powered to detect an effect size difference of .35 (2 raw score points) or larger on production.

$$\begin{aligned} \text{Likelihood of a Correct Production} &= \text{TestPoint} * \text{TreatmentCondition} \\ &\quad + (1|\text{item}) + (\text{clause type} |\text{subject}) \\ \text{Structural Sensitivity} &= \text{TestPoint} * \text{TreatmentCondition} \\ &\quad + (\text{clause type} |\text{subject}) \end{aligned}$$

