In the somewhat likely event that the interaction between time point and treatment is not significant, we can directly test for treatment efficacy by comparing the effect of treatment on the treated vs. untreated structures. We expect that the model estimate for Treated or Untreated clause will be significant at p<0.05 level, favoring the treated clauses, demonstrating that treatment was effective and ruling out maturational effects.

$$\begin{aligned} \text{Likelihood of a Correct Production} &= \text{TestPoint} * \text{TreatedOrUntreated} \\ &\quad + (1|\text{item}) + (\text{clause type} |\text{subject}) \\ \text{Structural Sensitivity} &= \text{TestPoint} * \text{TreatedOrUntreated} \\ &\quad + (\text{clause type} |\text{subject}) \end{aligned}$$

Aim 2. Determine whether the influence of delivery method (illustrated syntax stories or recast therapy) on dose delivered (number of exposures to the target) is of sufficient magnitude that changes in child outcomes are observed when treatment is delivered by caregivers.

We will first determine whether dose differs across the two at-home conditions. We will carry out an unpaired two-tailed t-test comparing the estimated dose delivered for each condition. We anticipate that the two conditions will differ and that the distributions will show low degrees of overlap (p<.05, d>.5).

To test the key question in Aim 2, we will test for a dose by test point or dose by treatment condition by test point interaction for stories at home and recasts at home conditions. Well-matched groups at pretest will be evident if the two conditions do not differ at pre-test. If one treatment condition is more effective than the other, this should be evidenced by an interaction between test point and treatment contrast effects that are significant at the p<.05 level; if, as we hypothesize, dose is a critical component of this difference, a two- or three-way interaction between time and dose or between time, treatment and dose will be observed. We would interpret the two-way interaction as indicating that dose, rather than treatment is critical for obtaining the key outcomes. A three- way interaction suggests that the delivery method modifies the effectiveness of the total dose.

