$$\begin{aligned} \text{Likelihood of a Correct Production} &= \text{TestPoint} * \text{TreatmentCondition} * \text{EstimatedDose} \\ &\quad + (1|\text{item}) + (\text{clause type} |\text{subject}) \\ \text{Structural Sensitivity} &= \text{TestPoint} * \text{TreatmentCondition} * \text{EstimatedDose} \\ &\quad + (\text{clause type} |\text{subject}) \end{aligned}$$

In the event that the interaction between time point and treatment is not significant, we can directly test for treatment efficacy by comparing the effect of treatment on the treated or untreated structures. We expect that the model estimate for Treated vs. Untreated clause will be significant at p<0.05 level, favoring the treated clauses, demonstrating that treatment was effective and ruling out maturational effects.

$$\begin{aligned} \text{Likelihood of a Correct Production} &= \text{TestPoint} * \text{TreatedOrUntreated} \\ &\quad + (1|\text{item}) + (\text{clause type} |\text{subject}) \\ \text{Structural Sensitivity} &= \text{TestPoint} * \text{TreatedOrUntreated} \\ &\quad + (\text{clause type} |\text{subject}) \end{aligned}$$

Power Analysis for Production

Power analyses were carried out using Monte Carlo simulation (5,000 iterations) via SAS 9.4 and PROC GLIMMIX using residual pseudolikelihood estimation of a binary logistic mixed effects model with item responses (n=20) nested within tests (n=4 representing test point and clause type repeated measures) that are nested within children (n=120) who have been randomly assigned to treatment conditions, counterbalanced across the 2 clauses. Random effects are included for items within clauses, as well as four correlated child-level random effects (i.e., for each of the four repeated measures). A single model was used to estimate power in alignment with the overall design of the study in which children are randomly assigned to one of FOUR conditions. Power for the more focused models described above can be inferred from the power estimates for the treatment contrasts below. By adopting this randomization scheme and model design, we retain the ability to test unplanned contrasts that go beyond the planned analyses for the Aims if we so chose (e.g., recasts in the lab vs. recasts at home) in order to carry out secondary analysis associated with cost effectiveness, dose, or home environment.

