Test scores were simulated based on means and standard deviations of pretest and posttest scores from a previous study. Pretest scores for both clauses were sampled from a Normal distribution with $M=3.0$ and $SD=2.5$, rounding to the nearest integer, with a minimum score of 0 and maximum score of 7 items correct (corresponding to the >40% correct study eligibility criteria). Posttest scores for untreated clauses were sampled from a Normal distribution with a correlation of .90 with pretest scores and $M=3.0$ and $SD=2.5$, rounding to the nearest integer, with a minimum score of 0. Posttest scores for treated clauses were sampled from a Normal distribution with a correlation of .90 with pretest scores, rounding to the nearest integer, with a minimum score of 0, and $M=5.5$ and $SD=4.0$ for the syntax stories at home condition ($ES=+1.0$), $M=4.0$ and $SD=4.0$ for the parent recasts condition ($ES=+0.4$), $M=6.0$ and $SD=3.5$ for the syntax stories in the lab condition ($ES=+1.2$), and $M=8.0$ and $SD=3.5$ for the lab recasts condition ($ES=+2.0$).

Based on the above effect size estimates, power for detecting main effects in Aim 1 exceeds .95 for the syntax stories at home, syntax stories in the lab, and lab recasts. Power is .61 for detecting main effects of parent recasts (i.e., the effect of parent recasts would need to exceed .50 to be detected with 80% power). Power for treatment effect contrasts is .75 to detect differences in syntax stories at home and parent recasts effects, .90 to detect differences in parent recasts and syntax stories in the lab effects, and .99 to detect differences in parent recasts and lab recasts effects. Other contrasts (e.g., syntax stories at home vs. syntax stories in the lab) have power less than 80% if the expected effect sizes hold true (i.e., +1.0 vs. +1.2); differences in effects would need to exceed 0.35 logits (2 raw score points) in order reach statistical significance with 80% power.

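### Aim 1 hypothesises that the two in-lab treatments are equally effective, but ties this only to a non-significant interaction, with no margin or interval

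*Protocol*

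**What the plan says.** In the Protocol, Analytic Approach, Aim 1, the key contrast is lab stories against lab recasts, tested by the interaction of test point with treatment condition at the 5% level. The hypothesis is equality, and the result linked to it is: "if, as we hypothesize, the two conditions are equally effective there will be no significant interaction between test point and treatment". The next sentence gives a detectable difference: "We are powered to detect an effect size difference of .35 (2 raw score points) or larger on production". The same interaction model is set for Structural Sensitivity, and the Analytic Approach says of production and comprehension that "we make similar predictions as to the effect of treatment on each outcome measure".

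The plan expects that it may well meet a null. The follow-on step opens: "In the somewhat likely event that the interaction between time point and treatment is not significant". It then compares treated with untreated clauses, in a model without a treatment condition term.

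A preliminary check that dose was controlled in the two lab arms anticipates that "the distributions will show high degrees of overlap ($p>.5$, $d<.3").

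**The concern.** A test that can only reject equality cannot support it. A smaller or noisier trial makes the predicted result more likely, so the hypothesis is favoured by poor precision. Nothing else in the document fills the gap:

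- The 2 raw points are a difference detectable by a superiority test and are not used as a margin.
- The treated-versus-untreated fallback asks whether treatment worked, not whether the two arms are alike.
- For eye tracking, the Protocol gives only detectable effects.

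At stake is the reading of Aim 1's hypothesised result. Without a pre-set rule, a null can be reported as support for equal effectiveness when the data cannot exclude a sizeable difference. The plan's own inputs make this a live possibility, because Power Analysis for Production simulates the two lab arms as different: post-test means of 6.0 and 8.0, with effect sizes given as "for the syntax stories in the lab condition ($ES=+1.2$), and $M=8.0$ and $SD=3.5$ for the lab recasts condition ($ES=+2.0").

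**Working it through.** **Inputs.** From Power Analysis for Production:
- pretest mean 3.0, SD 2.5, limited to 0–7;
- treated post-test mean 6.0 (lab stories) and 8.0 (lab recasts), SD 3.5 in both;
- untreated post-test mean 3.0, SD 2.5;
- pre-post correlation .90;
- 2 raw points detectable with 80% power.

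The power model has items and tests "that are nested within children (n=120) who have been randomly assigned to treatment conditions", so 120/4 = 30 per arm. The design section says "thus we expect 35 participants per condition". Equal allocation and a two-sided 5% test are assumed.

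**The plan's own figure.** The 2 points come from a mixed-model simulation whose variance components are not given, so they cannot be reproduced exactly. The closed form (1.960 + 0.842) × SD × √(2/30) brackets them:
- change-score SD √(3.5² + 2.5² − 2 × 0.9 × 3.5 × 2.5) = 1.66 gives 1.20 points;
- post-test SD 3.5 gives 2.53 points.

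**Precision implied by that figure.** SE = 2/(1.960 + 0.842) = 0.714 at 30 per arm, and 0.714 × √(30/35) = 0.661 at 35.

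**Chance of a non-significant result.** With the implied SE this is Φ(1.96 − δ/SE) − Φ(−1.96 − δ/SE), where δ is the true difference in points. For δ = 1 at 30 per arm, δ/SE = 1.40 and the result is .712. For δ = 2, δ/SE = 2.80 and the result is .200.

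As a second route, scores were simulated from the inputs above (20,000 trials per cell, rounded, post-test limited to 0–20) and compared by two-sample t-tests on change:

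| True difference | Per arm | Raw, treated | Raw, treated minus untreated | Empirical logit, treated | Empirical logit, treated minus untreated | Implied SE |
|---|---|---|---|---|---|---|
| 1 point | 30 | .489 | .604 | .555 | .741 | .712 |
| 2 points | 30 | .024 | .079 | .062 | .288 | .200 |
| 1 point | 35 | .420 | .546 | .494 | .702 | .672 |
| 2 points | 35 | .012 | .047 | .033 | .222 | .143 |

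**What a null can hide.** At 30 per arm the simulated SE of the raw difference is .471 (treated) or .552 (treated minus untreated). The 95% half-widths are .94 and 1.10 points, or 1.96 × 0.714 = 1.40 on the implied SE. A just non-significant estimate equals the half-width, so its interval runs from 0 to twice that: 1.88 to 2.80 points. The assumed stories gain is 6.0 − 3.0 = 3.0.

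**Dose check.** If doses are identically distributed (normal), the p-value is uniform, so p > .5 is missed 50% of the time at any sample size. The condition d < .3 is missed 25% of the time at 30 per arm (1 − .751) and 21% at 35 (1 − .787).

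**The case against.** The strongest reply is that the sentence is a prediction, not a decision rule. The plan never says that a null will be taken as proof of equality. Aim 1 is framed as a test for differences, that test is valid, and the step after a null concerns efficacy. The plan also discloses its sensitivity by stating the detectable difference right after the hypothesis. This stands as a description of the wording. It does not close the gap: equality is the stated hypothesis, the null is the only result linked to it, and no interval or margin is named. Deferral to a separate SAP is a weak defence, since the version note says this document includes one.

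Three points on size also have force:

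- No passage calls a 1-point difference important. For the plan's own 2-point lab difference, three of the four simulated measures miss it only 2% to 8% of the time at 30 per arm.
- The implied SE takes 2 points as the exact 80%-power difference, but the plan equates 2 points with 0.35 logits, while 6/20 against 8/20 is ln(8/12) − ln(6/14) = 0.44 logits. The upper end of the range is therefore uncertain.
- The dose check states an expectation and names an effect size beside the p-value, so it is a secondary matter.

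**Conclusion.** The concern holds and should be fixed. A non-significant interaction would not separate equal effectiveness from a true difference of about 1 point, which is missed 49% to 74% of the time at 30 per arm and 42% to 70% at 35. A true 2-point difference is missed 2% to 29% and 1% to 22% of the time. These figures are illustrations from t-tests on change and from the SE implied by the plan's detectable difference; they are not output of the planned mixed model. The conclusion does not depend on the exact values. The planned model and test are sound; the defect is confined to how a null result will be interpreted, for production and for Structural Sensitivity.

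**What to change.** Add to Aim 1: *A non-significant test point by treatment interaction will not be read as equal effectiveness.* For each outcome, report the lab recasts minus lab stories difference in gain with its confidence interval on the scale of the planned model and, for production, also in raw points.

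If equivalence on production is to be claimed, require the 90% interval to lie inside a margin justified and fixed before outcomes are seen; otherwise call the result inconclusive or different. The 2-point detectable difference is two-thirds of the assumed stories gain (2/3.0), so it needs its own justification before it can serve as a margin. For Structural Sensitivity, make no equality claim unless a margin is justified. For the dose check, report the mean difference in dose with its interval rather than relying on p > .5.

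The cost is wording, one interval per outcome, and the work of justifying a margin if equivalence is to be claimed. The downside is that some results will be labelled inconclusive. With truly equal arms, power to show equivalence on the implied SE is 2Φ(margin/SE − 1.645) − 1. Together with the raw-score simulations, this gives:

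- an illustrative 1-point margin is met in about 0% to 35% of trials at 30 per arm (0% to 47% at 35);
- an illustrative 2-point margin is met in about 75% to 99% (83% to over 99% at 35).

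No extra participants are needed if an inconclusive result is accepted.

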Simulations that include dose indicate power of .93 for models that include dose and time. Effects of treatment, dose, and power combined are not detectable because this estimation of dose confounds the distribution of dose with treatment delivery approach, as we hypothesize in the strategy. It suggests that three-way interactions will only be detectable if the delivery method modifies the benefit obtained from each exposure to the target form.

Power Analysis for Eye Tracking

Power analyses were carried out using G*Power (Faul, Erdfelder, Lang, & Buchner, 2007). Our preliminary data focused on eye-movements during a single test point, thus we do not have relevant estimates of fixation changes at multiple time points or following interventions. Consequently, we based our sample size on power analyses for production ($n=120$) and calculated the smallest changes in Structural Sensitivity that will be detectable with varying levels of power.

In our preliminary data ($n=15$), children with DLD revealed $M = 0.02$ and $SD = 0.17$ in the late window. With the proposed sample size, effect sizes of $d=.30$ will be detectable with 80% power, $d=.34$ with 90% power, and $d=.42$ with 99% power. These correspond to increases in Structural Sensitivity of $M=.05$, $M = .06$, and $M = .07$ respectively. For reference the TD children in our Preliminary Data have a Structural Sensitivity score that is $M=.29$ larger than that of the children with DLD. Based on this benchmark, improvements across time points that are 17-24% in magnitude would be detectable in the current design. This suggests that this study is adequately powered to detect relatively small changes in linguistically mediated fixations.

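### Aim 2 lets either of two terms from one full-factorial model, with contrast coding not fixed, support the dose hypothesis: the two-way term has no settled meaning or power, and the either-term rule has a false-positive rate of about 7–10%

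*Protocol*

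**What the plan says.** All references are to the Protocol.

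- **Key test.** The Aim 2 text under Analytic Approach sets the test for the two caregiver-delivered arms: "we will test for a dose by test point or dose by treatment condition by test point interaction for stories at home and recasts at" (quote cut short). If dose is a critical component, the plan expects that "a two- or three-way interaction between time and dose or between time, treatment and dose will be observed".
- **Reading of the two-way term.** "We would interpret the two-way interaction as indicating that dose, rather than treatment is critical for obtaining the key outcomes". The three-way term is read as delivery method changing what a given total dose achieves.
- **Model.** One outcome model is written for this question: TestPoint*TreatmentCondition*EstimatedDose plus random effects. No model without the three-way product is given.
- **Inference.** Analytic Approach says that "parameter-specific p-values will be estimated with degrees of freedom determined through Satterthwaite approximation". The level appears in the sentence on the treatment contrast, "an interaction between test point and treatment contrast effects that are significant at the p<.05 level". No other level is given for the dose terms, so .05 is taken to apply to each.
- **Power.** Power Analysis for Production states: "Simulations that include dose indicate power of .93 for models that include dose and time". It adds that the combined treatment-and-dose effect could not be detected. Just before this it says that the planned analyses were run on the simulated data.

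**The concern.** When a model contains the three-way product, its lower-order dose-by-time coefficient is not automatically the overall dose effect. What it estimates depends on how treatment condition is coded. Under 0/1 coding it describes one arm and says nothing about the other, so it cannot separate dose from treatment. Because the coding is open, the same data could support Aim 2's central hypothesis under one choice and fail to do so under another.

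Two further consequences follow. Accepting either of two terms at .05 as support for dose being critical gives two chances at a positive result. And a reader cannot tell which test the .93 describes, so cannot judge whether the planned test is adequately powered.

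**Working it through.** **Inputs from the Protocol.** Table 1 at-home doses (minimum, quartiles, maximum): recasts 60/96/192/320/960; stories 60/240/460/960/1680. Gain per exposure is uniform on .0005 to .006 in both arms. Pretest is Normal(3.0, 2.5), rounded and limited to 0–7, with 20 items per test. The power work has items "nested within children (n=120) who have been randomly assigned to treatment conditions, counterbalanced across the 2 clauses", so 120/4 = 30 per arm; 35 completers per arm are planned.

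**Assumptions.** Dose is uniform between the Table 1 points. Only the treated clause is simulated. Models are simplified: either a binomial-logit mixed model with a random child intercept, or least squares on change scores. The Protocol does not give the residual noise or random-effect variances of its dose simulation.

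**1. The plan's own .93.** A dose-and-time model without treatment gives .99 (30 per arm) and .996 (35 per arm) in the logit model. On change scores with binomial item noise it gives .95 and .97. With an assumed added noise SD of 2.5 on change scores it gives .936 at 30 per arm. The full factorial with stories as reference or sum coding, logit model, 35 per arm, gives .91–.95. So .93 is not reproduced exactly, and several candidate tests lie near it.

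**2. What the two-way term estimates.** Let bR and bS be the dose slopes of change in the recast and story arms.
- 0/1 coding, recasts as reference: two-way = bR, three-way = bS − bR.
- 0/1 coding, stories as reference: two-way = bS.
- Sum coding: two-way = (bR + bS)/2, whichever arm is named first.

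**3. Why the choice matters here.** Table 1 gives dose means of (78+144+256+640)/4 = 279.5 for recasts and (150+350+710+1320)/4 = 632.5 for stories, with SDs of about 238 and 464. With equal residual SD and equal n, the slope's standard error is inversely proportional to the dose SD, so SE(bR)/SE(bS) = 464/238 = 1.95. Take power .83 with stories as reference, that is z = 1.96 + 0.954 = 2.914. For the same true slope:
- recasts as reference: z = 2.914/1.95 = 1.494, power .32;
- sum coding: SE factor ½√(1 + 1.95²) = 1.096, z = 2.660, power .76;
- additive model (common slope): z = 2.914 × √(1 + 1/1.95²) = 3.275, power .91.

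**4. Simulated power, 30 per arm.**

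| Dose-by-time test | Logit mixed model | Change score, item noise | Separate change-score run |
|---|---|---|---|
| Full factorial, recasts reference | .27–.28 | .36 | .42 |
| Full factorial, stories reference | .85 | .83 | .84 |
| Full factorial, sum coding | .86 | .77 | .82 |
| Additive, no three-way product | .97 | .91 | .92 |

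At 35 per arm the first three rows are .34–.38, .91–.93 and .95 in the logit model, and .42, .88 and .83 on change scores with item noise. In the logit model at 30 per arm, the two reference choices gave different verdicts in 65% of simulated trials. Three-way power was .00 (logit) to .06–.15 (least squares), in line with the Protocol's own remark.

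Sensitivity: the empirical-logit scale gives .34, .68 and .68 for the first three rows. Pooling an unchanged untreated clause gives .23, .65 and .54. With less noise the gap narrows: at an added SD of 1.5 and 30 per arm, recasts as reference gives .61 and stories .98.

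**5. False positives with no dose effect.** The correlation between the two terms, in absolute value and with v = 1.95² = 3.80, is √(v/(1+v)) = .89 with recasts as reference, √(1/(1+v)) = .46 with stories, and (v−1)/(v+1) = .58 with sum coding. The bivariate normal chance that at least one exceeds 1.96 in absolute value is then .071, .092 and .088. Simulation gives .063–.080 (recasts), .087–.101 (stories) and .079–.094 (sum). Independence would give 1 − .95² = .0975. Each single test stays at about .04–.06, and a joint 2-df F test gives .052.

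**The case against.** The strongest reply is that much of this is detail usually settled in programming. Sum coding, or Type III tests with class variables, makes the two-way term an average slope free of the reference arm. The two terms also have different stated readings, so they are not simply one claim tested twice. This is a self-described Phase I behavioural trial. And the simulations use one clause and simplified models, so they are not this plan's actual power.

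Much of that stands. A reader might infer that the result always depends on the reference arm; that is so only under 0/1 coding, which the Protocol neither specifies nor excludes. A reader might infer that the dose test itself has an inflated error rate; it does not, because only the either-term rule exceeds 5%. A reader might infer that .93 came from a different model. The wording invites that, but the Protocol says the planned analyses were run, reports on the combined term as well, and full-factorial values of .91–.95 surround .93.

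What does not stand is that nothing needs changing. The Protocol's version note says that it includes the statistical analysis plan. It prescribes single-parameter p-values, names one model, counts either term as a sign that dose is critical, and fixes a reading of the two-way term that is wrong under a common coding. That is a stated rule that can mislead when followed, not merely an omitted detail.

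**Conclusion.** The concern holds in this form; it should be fixed.

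- **Meaning and power of the two-way term.** With coding open, it may be one arm's slope or an average of two. Under 0/1 coding it cannot support the plan's reading. Simulated power is roughly .3–.45 with recasts as reference, against mostly .8–.9 with stories as reference or sum coding. These sizes rest on the Table 1 doses, the treated clause, the simplified models and assumed noise. The direction persists on other scales and with both clauses pooled, though the levels fall; with little noise the gap narrows.
- **Error rate.** The either-term rule runs at about 7–10%, with single checks as low as 6.3%. Each term alone holds about 5%.
- **The .93.** It is not tied to a defined term of the written model, and these simulations do not support it for the two-way term with recasts as reference at the noise levels implied by 20-item tests. The documents do not show that it is wrong or that it came from another model: the inputs needed to reproduce it are not given.

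**What to change.** 1. Test the dose hypothesis once. Either use a joint 2-df Wald or F test of TestPoint × EstimatedDose and TestPoint × TreatmentCondition × EstimatedDose, or name as the single primary dose test the dose-by-time term from TestPoint*TreatmentCondition + TestPoint*EstimatedDose. A likelihood-ratio test is suitable only if both models are fitted by true maximum likelihood, not by the residual pseudolikelihood named for the power model.
2. Estimate the common dose slope from that additive model. It does not depend on the reference arm, held about 5% (.053) in simulation, and had power of .91–.97 at 30 per arm in the set-ups tabulated above (.81 on the empirical-logit scale).
3. Keep treatment-by-time in the model. With no dose effect but a real arm difference, a dose-and-time model without treatment rejected in about 10% (logit) to 21–24% (least squares) of runs.
4. Report the three-way term separately, as the test of a different benefit per exposure, and state the contrast coding.
5. Re-run the dose simulation for the chosen test, name the term, and restate the .93, which may go up or down.

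The cost is a few sentences in the analysis section and one re-run of an existing simulation. No extra data or children are needed for the change itself, but it must be made before the outcome data are examined, because choosing the coding afterwards could choose the conclusion.
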